### **Detailed Description of Measures**

#### **Measures/Instruments included in the assessment battery**

1. **The Medical Outcomes Study (MOS) SF-12**: The SF-12 (39), a widely used standardized instrument with strong psychometric properties, will be used to assess self-perceptions of general health functioning across multiple dimensions (including general, physical and emotional/psychiatric functioning). The SF-12 has shown good internal, consistency, stability, and concurrent validity in outpatients with serious mental illness. (instrument is attached to this protocol).

2. Illness Management Self-Efficacy: This questionnaire is based on the items used in the original Chronic Disease Self-Management Program (CDSMP) as part of that group's extensive evaluation of the curriculum (41). The original CDSMP measure has been shown to have strong test-retest reliability and internal consistency as well (41).

3. Patient Activation Measure: This 13-item questionnaire measures an individual's perceived ability to manage his or her illness and health behaviors and act as an effective patient. The measure has demonstrated reliability and validity (36).

4. Measure of Self-Management Behaviors: This questionnaire is based on the items used in the original CDSMP as part of that group's extensive evaluation of the curriculum (41). The original CDSMP measure has been shown to have adequate psychometric properties; the range of test-retest coefficients for the original illness management scales was .56 to .92, with internal-consistency coefficients ranging from .70 to .75.

5 Morisky Medication Adherence Scale: This 8 item self-reported medication adherence scale was developed from a well validated 4-item scale and supplemented with additional items to better capture barriers surrounding adherence behavior. This new scale has demonstrated psychometric properties (43).

6. Basis 24 – Modified: The Basis 24 – Modified is a self-report measure that asks participants about their symptoms and functioning within the time period of a week. Response sets range from “no difficulty – extreme difficulty”, “none of the time – all of the time”, and “never – always”, each with 5 options.

7. Service Utilization and Resources Form (SURF): The SURF has been used successfully in several VA studies to assess service utilization relating to a range of medical services including ER, inpatient and outpatient services (40).

8. The Mental Illness Research, Education and Clinical Center (MIRECC) Demographic Form: The MIRECC Demographic form will be used to gather basic demographic information from the participant, including age, race, gender, living arrangement, etc.

9. Maryland Assessment of Recovery Scale : The MARS a 25-item self-report measure of recovery. Items are rated on a 5-point Likert scale (strongly disagree to strongly agree). The MARS has been shown to have good internal consistency (alpha=.95) and test-retest reliability (r = .868)

10. The Repeatable Battery for the Assessment of Neuropsychological Status (RBANS): The Repeatable Battery for the Assessment of Neuropsychological Status (RBANS) is a comprehensive neuropsychological screening battery that assesses memory, language, visuo-spatial/constructional ability, and attention. The RBANS has been shown to perform well as a clinical screening test and as an outcome measure for clinical trials in schizophrenia. As cognitive functioning may relate to study outcomes, RBANS scores will be used in exploratory analyses focusing on the relationship between various cognitive skills and related study outcomes. We will be using an abbreviated version.

11. Insomnia Severity Index (ISI): This measurement is a brief assessment (7 items) inquiring about the severity of a person's insomnia and sleep problems and patterns. It also questions their satisfaction level with their sleep, how worried or distressed they are, and how much they feel it is interfering in their daily functioning. All responses are on a 4 point Likert scale.

12. Medical Conditions (MCON): A series of interview items drawn from the National Health and Nutrition Examination Survey III solicits the presence of lifetime and current co-occurring medical conditions and whether the patient is currently receiving treatment.

13. PAIN Measure: This measure was created for this study. It consists of 4 Likert response questions from the Pain Numeric Rating Scale which is available on the Department of Veterans Affairs website under Clinical Tools for Pain Management that inquires about a person's level of pain. It also consists of a one yes/no question and one multiple choice response questions where both inquire about treatment of pain.

14. Participation with Services: This questionnaire was created for this study. It is comprised of yes/no and Likert-response item questions concerning participants' exposure to and involvement in peer facilitated groups or individual encounters with peer-counselors that focus on both mental health as well as physical and medical health and wellness.

15. Substance Use and Health Behaviors (SUHB): This instrument inquires about the use of substances and the effects on healthy behaviors, specifically illicit drugs, alcohol, tobacco, and caffeine. It also queries about the treatment for substance use or abuse, and regular physical activity and exercise.

16. Multidimensional Health Locus of Control (HLOC): An 18 item questionnaire with responses ranging on a 6 point Likert scale from Strongly Disagree to Strongly Agree that asks about self-perceived control over one's health, illnesses, and ability to take an active role in one's health.

17. General Medical and Psychiatric Services (GMED): This assessment measures how frequently participants utilize general health services, including primary medical doctors, specialists, emergency services, mental health services, and inpatient hospitalizations.

### **Effectiveness Trial Assessment/Interview Study Schedule**

	Consent	Randomization	Post-treatment	3-month Follow-up	Post-Trial Interview (N=20)
Assessments:					

 
• The Medical Outcomes Study
 
• Illness Management Self-Efficacy
 
• Patient Activation Measure
 
• Measure of Self-Management Behaviors
 
• Addiction Severity Index (ASI)
 
• Morisky Medication Adherence Scale
 
• Basis 24 Modified
 
• Service Utilization and Resources Form (SURF)
 
• Maryland Assessment of Recovery Scale (MARS)
 
• General Medical and Psychiatric Health Services (GMED)
 
• Multidimensional Health Locus of Control (HLOC)
 
• Substance Use and Health Behaviors (SUHB)
 
• Participation in Other Services (POS)
 
• PAIN Measure
 
• Medical Conditions (MCON)
 
• Insomnia Severity Index (ISI)
 
 
 
• The Repeatable Battery for the Assessment of Neuropsychological Status (RBANS) (randomization only)
 
• MIRECC Demographics
 
	R	R	R	R	

(randomization only)					
Interview					R

### **Treatment Procedures**

This is not a treatment study. All assessments and group sessions will be conducted by Research Assistants carefully trained on all study-related assessments and the manualized study intervention.

### **Staff Training/Fidelity Monitoring**

#### ***Living Well Interventionist Training and Fidelity Monitoring***

Our research team, including Drs. [name] and [name] has extensive experience developing psychosocial treatments and ensuring their fidelity. Drs [name] also has extensive experience training peer providers. All study interventionists (both peer and professional) will receive training that will include a thorough orientation to the *Living Well* curriculum and manual. This will include review of videotaped sessions of the intervention (created during our pilot work) and opportunities to practice and refine the skills needed to deliver the *Living Well* intervention. Our training includes modeling, role-plays, and practice facilitating mock group sessions. The peer interventionists will receive additional training sessions that are designed to enhance mental health peer providers' knowledge and further the development of their skills that will aid them in co-facilitating the *Living Well* Intervention. The training will be delivered in 3 full days and will cover a variety of topics including: Developing and using one's own recovery and wellness management story as a tool to assist others; strategies for effective communication; confidentiality/boundaries/dual relationships; advocacy; accessing and utilizing VA and community resources; suicide prevention awareness; group facilitation skills; and cultural competence.

To maximize the use of modeling and optimize peer support, all peer providers will have a co-occurring chronic medical condition. Non-peer co-facilitators will be selected from our pool of research interventionist all of whom have prior experience conducting psychosocial interventions with individuals with serious mental illness. If possible, we will select those who are living with a chronic medical condition to further maximize the effects of modeling and support based on a shared experience. To aid with ongoing supervision and fidelity monitoring, we will develop a structured supervision strategy that includes audio/videotaping of all session, weekly supervision conducted by one or more of the investigators, and objective assessment of adherence and competence. To complete this aspect of fidelity assessment we have developed a facilitator adherence and competence rating scale. The adherence scale contains items (scored "excellent," "acceptable" or "unacceptable") assessing the presence or absence of core features of the intervention including instruction in and practice behavioral action planning, in-session practice of self-management techniques, and use of problem solving. The Competence scale contains items assessing more process-oriented aspects including effective use of peer modeling, use of confidence building techniques, and reinforcement and encouragement of self-management skills. Ratings will be completed by an independent rater from a randomly selected 25% of each peer/provider pair's audio/video-recorded sessions. A second rater, will independently rate a subset

of the tapes to assess inter-rater reliability. Both of these raters will be study staff directly involved with this project and listed on the protocol.

### **Medical Illness Education and Support Group (comparison condition) Training and Fidelity Monitoring**

Study interventionists delivering the medical illness education and support comparison condition will all have prior experience conducting psychosocial/educational interventions with individuals with SMI. As with the interventionists delivering *Living Well*, they will receive training that includes an orientation to the medical Illness education and support group manual developed for this study. They will also receive ongoing supervision. To monitor fidelity and ensure that the two conditions remain distinct we will also video tape sessions and use independent raters to complete an objective assessment of intervention adherence. The independent raters used for this study will be directly involved with this project and listed on the protocol. The adherence scale will include items assessing the presence of condition specified core elements such as review of common chronic illness challenges and discussion about related behavioral and lifestyle self-management techniques, and absence of core elements associated with the *Living Well* Condition (e.g. use of behavioral action planning and in-session practice of self-management techniques). Similar to the *Living Well* condition, ratings will be completed on a randomly selected 25% of sessions delivered across the trial for each provider.

### **Reportable Events**

All Unanticipated Problems, Serious Adverse Events and Deviations related to this study will be reported to the VA Central IRB within 5 business days of study staff becoming aware of the event. Adverse events that do not meet the criteria for reporting within 5 business days will be reported to the VA Central IRB at the time of continuing review in summary format.

### **Sample Size**

For EFFECTIVENESS TRIAL:

This Randomized Controlled Effectiveness Trial is powered to detect differences on the two primary outcomes: (1) significantly reduced proportion of participants with an ER visit at the 3-month follow-up assessment (6 months post randomization) in the Living Well condition versus control, (2) significantly improved health functioning at post-treatment in the Living Well condition versus control as measured by the SF-12.

ER Visits. In our prior pilot the proportion with an ER visit in the Living Well condition at the 3-month follow-up was 10.7% and in the control condition it was 27.6%. For this power calculation we assumed that the proportion with an ER visit in the Living Well condition at the 3-month follow-up will be 10.7%. However, since we have an active control in this proposal, we specify a lower percentage in the control condition (versus estimate from the pilot study) equal to 25%, and thus a 14.3 percentage point difference. With a two-tailed, alpha .05 level test, and power = .80 to detect this 14.3 percentage point difference we calculate that we will need n = 250 (125 per condition). The percentage point difference that can be detected could be somewhat higher or lower depending on the inter-correlations among the covariates and ER response variable. As proportion with an ER visit will be obtained from VA electronic medical charts for all randomized participants, loss to follow-up is not a significant concern for this outcome. This calculation is conservative -- we would actually have power equal to .80 to detect a smaller difference because the above calculation is based on a basic z-test of proportions, whereas the analysis model

specified above is more powerful. Calculation was performed using PASS version 11.0 (from NCSS, LLC) software. We acknowledge that use of the ER may be different in the VA context given the co-location of medical and psychiatric care, but as evidenced in our previous work (see section A.3), we found that veterans with SMI used the VA ER for medical care at rates comparable to (even greater than) those in our community sample. Specifically, the rate of use in the VA sample was 43% and the baseline rate in the Living Well sample was 31.3%.

SF-12 functioning scales. Effect sizes (ES, Cohen's d at post-treatment--3 months post-randomization) in our pilot clinical trial for the SF-12 physical, emotional, and general functioning scales were .55, .66, and .68. For H1 we assume a consent sample size equal to the sample size determined for H2 and calculated the power we will have to detect a moderate but significant ES = .40 (i.e. to detect means that are .4 standard deviations apart) between Living Well and the control condition. ES = .40 was also selected as the ES for this trial may be smaller than our prior trial because we are using an active control. We assume there will be 12% loss-to-follow-up at the post-treatment assessment, hence we have conservatively assumed a net sample size of  $250 * (1 - .12) = 220$  (110 per condition) for the SF-12 outcomes. With a two-tailed, .05 alpha level test, and average correlation among longitudinal measurements equal to .50, and post-attrition n = 220, we would have power = .89 to detect an effect size equal to .40. Calculation was performed using the Sampsii command (for repeated measures) in Stata version 10 (from Stata Corporation).

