### **Hypotheses**

The purpose of this study is to: 1. Complete an effectiveness trial of Living Well in the VA context, and; 2. Concurrently collect, in the context of a process evaluation, important contextual and cost information that can help speed throughout to public health impact.

For the remainder of this protocol all required descriptions will be presented first for the EFFECTIVENESS TRIAL and second for the PROCESS EVALUATION.

Objectives and hypotheses for the EFFECTIVENESS TRIAL:

Objective: Complete a randomized controlled effectiveness trial comparing Living Well to a general medical illness education and support group among SMI Veterans with co-occurring chronic medical conditions. Those receiving Living Well will demonstrate:

Hypotheses for EFFECTIVENESS TRIAL:

Primary Hypotheses (regarding functional and service-related outcomes)

Hypothesis 1: Improved general, physical, and emotional functioning post intervention.

Hypothesis 2: Lower rates of medical emergency room use for management of a chronic medical condition six months post randomization.

Secondary Hypotheses (regarding more proximal attitudinal and behavioral outcomes)

Hypothesis 3: Improved health-related self-efficacy and patient activation post intervention. Further, such improvements will mediate the effects of the functional and service outcomes specified above.

Hypothesis 4: Improved self-management behaviors post intervention. Further, such improvements will mediate the effects of the functional and service outcomes specified above.

Secondary Hypothesis (regarding retention of intervention effects)

Hypothesis 5: Sustained improvements across functional, attitudinal and behavioral outcomes for three months after completing treatment.

Objective for the PROCESS EVALUATION:

Complete a well specified process evaluation based on the RE-AIM evaluation framework to better understand contextual factors that can improve future adoption, implementation and sustainability of the Living Well intervention in the VA system of care. A cost analysis will also be completed as part of this effort.

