#### Data Analysis

##### FOR EFFECTIVENESS TRIAL:

Primary Hypotheses (regarding functional and service-related outcomes):

Hypothesis 1 (H1): Compared to those receiving a general medical illness education and support group, participants receiving Living Well will demonstrate greater improved general health functioning including both physical and emotional functioning.

To test the null hypothesis of no difference in improved general health functioning, we will use a longitudinal mixed effects model to compare change in mean physical and emotional health functioning from randomization to post-treatment. Regression equation (random effects not presented) at each time point will be:

SF12 function = Intercept + site + covariates + study condition + time + study-condition\*time + error

Notes: (1) Test of the null hypothesis of no difference in change from randomization to the post-treatment assessment will be conducted using a specified contrast. (2) "Study condition" is a dichotomous variable indicating study condition; (3) A random intercept and random slope (coefficient for time) will also be specified for the model; (4) The "time" variable will be entered as a continuous variable with possible values 0, 3, and 6 corresponding to the three assessment points (randomization, post-treatment, & 3-month follow-up); (5) The "covariates" terms represent adjustment for age, race, gender, and important potential confounders and will include Charlson comorbidity index score, chronic somatic illness

category, and any other covariate found to significantly differ at randomization (provided no significant collinearities are found). We are expecting few chance differences at randomization due to large sample size and random study condition assignment; (6) We have included a “site” term to adjust for site differences.

Hypothesis 2 (H2): Compared to the medical illness education and support group, the Living Well group will have a lower proportion of participants who will have had an emergency room visit for management of a chronic medical condition during the six months after randomization.

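### The SF-12 power of .89 does not follow from its stated inputs: at 110 per condition and a common correlation of .50, the planned change comparison gives .84

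*Protocol*

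**What the plan says.** The SF-12 paragraph of the Protocol's Sample Size section takes the 250 participants required for the emergency-room outcome. It then allows for dropout: "We assume there will be 12% loss-to-follow-up at the post-treatment assessment". That leaves 220, or 110 per condition. The target effect is .40 standard deviations. The remaining inputs are given as "With a two-tailed, .05 alpha level test, and average correlation among longitudinal measurements equal to .50", and the result is "post-attrition n = 220, we would have power = .89 to detect an effect size equal to .40". On the tool, the section says "Calculation was performed using the Sampsii command (for repeated measures) in Stata version 10". It gives neither the method (post-treatment only, change, or ANCOVA) nor the number of measurements before and after the start of treatment.

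The test being powered is in the Data Analysis section under Hypothesis 1. The model has site, covariates, condition, linear time over months 0, 3 and 6, and condition by time. Note 1 reads: "Test of the null hypothesis of no difference in change from randomization to the post-treatment assessment will be conducted using a specified contrast". The condition main effect is kept, so the groups are not constrained to be equal at randomization.

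**The concern.** The effect size, significance level, correlation and number per condition are all stated, so a reader should be able to recover the power. The only open choices are the method and the number of measurements. If no choice leads to .89, the figure conflicts with the inputs given beside it, and naming the missing options would not rescue it.

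This is the power claim for one of the trial's two primary outcomes. An overstated figure also hides how much the change comparison depends on the assumed correlation.

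**Working it through.** **Inputs** (Protocol, Sample Size): effect size .40 in raw standard deviations; two-sided alpha .05; correlation .50, taken as common to all pairs of measurements; n = 110 per condition, from 250 × (1 − .12) = 220.

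**Formula.** Power = Φ(.40·√(n/2)/√v − 1.96). The variance factor v, for p measurements before and q after, is:

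- post only: v = (1 + (q−1)r)/q
- change: v = (1 + (q−1)r)/q + (1 + (p−1)r)/p − 2r
- ANCOVA: v = (1 + (q−1)r)/q − r²/[(1 + (p−1)r)/p]

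**Trying to reproduce .89 at n = 110.** Here .40·√55 = 2.966.

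- One pre, one post, change or post only: v = 1, and Φ(2.966 − 1.960) = Φ(1.006) = .843.
- One pre, one post, ANCOVA: v = 1 − .25 = .75, and Φ(2.966/.866 − 1.960) = Φ(1.465) = .929.

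| Pre / post | Post only | Change | ANCOVA |
|---|---|---|---|
| 1 / 1 | .843 | .843 | .929 |
| 1 / 2 | .929 | .929 | .987 |
| 1 / 3 | .953 | .953 | .996 |
| 2 / 1 | .843 | .929 | .953 |
| 2 / 2 | .929 | .987 | .996 |

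The remaining combinations up to three pre and three post are also either .843 or at least .929. The stated .89 lies in the gap, 4.7 points above the lower value and 3.9 below the upper. Using the t distribution barely changes this (.840 for v = 1, .927 for v = .75).

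**What would give .89.** Since z(.89) = 1.227, the required factor is v = (2.966/(1.960 + 1.227))² = .867.

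- Change 1/1: r = 1 − .867/2 = .57. ANCOVA 1/1: r = √(1 − .867) = .37. Neither is .50.
- Change 1/1 at r = .50: n = 2 × (3.187/.40)² = 126.9 per condition. Power rounds to .89 for 125 to 129 per condition.
- Change 1/1 at r = .50 and n = 110: effect size = 3.187 × √(2/110) = .430.
- At the pre-attrition 125 per condition, change or post only gives Φ(.40·√62.5 − 1.960) = Φ(1.202) = .885. So the 12% loss may not have been carried into the calculation.
- ANCOVA with the loss taken twice (110 × .88 = 96.8 per condition) gives .895, which also rounds to .89. The cause therefore cannot be identified from the protocol.
- A one-sided change test gives .907, and ANCOVA at alpha .025 gives .882. Each contradicts a stated input.

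**The planned linear-time model.** Take compound symmetry with r = .50, 110 per condition and the condition main effect kept. The fitted month-3 contrast is then half the month-0-to-6 difference in change. Hypothesis 5 expects "Sustained improvements across functional, attitudinal and behavioral outcomes for three months after completing treatment". If the group difference is 0, .40 and .40 at months 0, 3 and 6, the contrast estimate is .20, its variance is (1/4)(2/110) = .00455, the ratio is 2.966, and power is again .843. This depends on the assumed month-6 difference: power is .32 if that is .20, and above .99 if it is .80.

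**Sensitivity to the correlation** (change 1/1, n = 110): .773 at r = .40, .807 at .45, .843 at .50, .878 at .55 and .913 at .60.

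**The case against.** The strongest reply is that the protocol says "average correlation among longitudinal measurements equal to .50", and an average allows the individual correlations to differ. They need not differ by much. With one pre and two post measurements and the change method, pre-post correlations of .46 and a post-post correlation of .58 average .50. They give v = (1 + .58)/2 + 1 − 2(.46) = .87 and power .889. Correlations of .50 (months 0 and 3), .58 (3 and 6) and .42 (0 and 6) give the same result. With two pre and two post measurements, .41 across periods and .68 within periods give .892. On this view the figure is under-described rather than wrong.

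This stands to the extent that such a route cannot be excluded. It does not rescue the figure as written. The protocol states none of these correlations, and each pattern averages in a month-6 or consent assessment that the month-0-to-3 comparison does not use. For that comparison alone, power stays at .843 when the month 0-3 correlation is .50, and falls to .814 when it is .46.

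A second reply is that .84 also rests on assumptions, because the mixed model's power moves widely with the month-6 difference. That is correct and should be disclosed. The value .84 is what the protocol's own inputs give for a change comparison, and it agrees with the mixed model when the effect is fully sustained.

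A third reply is that nothing in the design changes. This is largely true and limits the weight of the point.

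**Conclusion.** The concern holds. Under a common correlation of .50, the stated .89 cannot be obtained at 110 per condition by post-only, change or ANCOVA calculations with up to three pre and three post measurements. For the change comparison closest to Hypothesis 1 the power is .84, so the risk of missing a .40 effect is about 16% (1 − .843) rather than 11%. ANCOVA would give .93, but that is not the analysis described.

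The conclusion rests on the common correlation and, for the linear-time model, on compound symmetry and a .40 difference held to month 6. That the figure does not reproduce under the common correlation is firm; the reason is not known, and an attrition allowance left out of the calculation is only one possibility. The practical effect is modest: the emergency-room outcome sets the sample size, and power at r = .50 remains above .80. The margin is thin, however, since a correlation of .40 would take the change comparison to .77.

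**What to change.** Rerun the SF-12 calculation and restate it in the Sample Size section as power .84 for an effect size of .40 at 220 participants. Equivalently, state a detectable effect size of .43 at power .89. Add one sentence naming the method, the number of pre and post measurements, the correlations and, if the linear-time model is the basis, the month-6 difference assumed. Quote .93 only if Hypothesis 1 is re-specified as a baseline-adjusted comparison. If .89 came from unequal correlations, print them and show that they apply to the planned contrast.

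The cost is one corrected figure, one sentence and a slightly less favourable power statement. No additional participants are needed.
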